9 STUDY ASSESSMENTS

9.1 Clinical evaluations

9.1.1 *Training and masking of MHGS evaluators*

The MHGS (**Figure 1**) will be used to measure clinical effectiveness of the Radiesse hand treatments by a masked evaluator performing live dorsal hand assessments. The MHGS is an ordinal scale and therefore ratings will be made based on a “snap-shot” at a time point and will not be based on a comparison to a pre-treatment photograph. The evaluator will remain masked throughout the study and blinded to knowledge of 0 to 3 repeat treatments during the study. Prior to study initiation, the masked evaluator will be trained and qualified by the study Sponsor to perform MHGS assessments. Training will consist of an instructional webinar and qualification will consist of the masked evaluator trainee scoring 2 25-subject photo booklets, at least 1 week apart for intra-rater weighted Kappa analyses prior to study initiation. Retraining will occur if a minimal weighted Kappa value is not achieved (≥ 0.60), with qualification required prior to screening subjects for the study, prior to initial X-ray and Radiesse treatment in the study. If a repeat hand treatment is scheduled during a study visit, the MHGS assessment will be completed prior to treatment. To ensure that the blind is maintained, subjects will have their upper body and face hidden behind a barrier screen with only their hand visible to the masked evaluator. Subjects will be asked to remain silent during the MHGS evaluation process. Masked evaluators will not be allowed to discuss treatment schedules with treatment investigators and study staff at the site, and will not enter data on case report forms (CRFs) that contain information that would break the blind.

9.1.2 *Evaluation of aesthetic improvement*

To assess the aesthetically pleasing aspect of the Radiesse hand treatment outcomes, subjects will perform self-assessments on the GAIS shown in **Table 1**. The GAIS is a relative scale, therefore the subjects will be asked to perform the rating compared to baseline pre-treatment photographs.

9.1.3 *Evaluation of hand function*

Subjective functional outcomes will also be assessed at baseline and at 1-, 3-, 6-, 7-, 12-, 13-, 18-, 19- and 24-months following initial injection of Radiesse using the validated MHQ (**Appendix C**). The MHQ is a patient-rated outcome tool based on psychometric principles that is capable of measuring health status domains that are important to patients with hand disorders.

[figure not shown]

9.1.4 Evaluation of hand X-rays

X-rays will be taken at a licensed radiographic imaging center. Plain anteroposterior and lateral views (**Figure 7**) of each hand will be taken at each required study timepoint. Digitized radiographic images will be transmitted to the imaging core lab to be assessed by 2 blinded, licensed radiologists. Copies of digitized X-rays will be sent from the imaging center to the investigational site and the Sponsor. The core lab will send confirmation of completed X-ray assessments to the investigational site and the Sponsor. The core lab will send results of the X-ray assessments to both the site and Sponsor within 21 days of receiving the digital X-rays from the imaging center. Results of the 6-month X-ray assessments will be used to determine the need to schedule X-rays prior to

the 12-month in-office follow-up visit. After completion of all 18-month follow-up visits at the site, both the local licensed imaging center and core lab will be informed of the total number of subjects who will be scheduled for 24-month X-rays. Only subjects who receive a total of 4 Radiesse hand treatments (initial, 6-, 12-, and 18-month treatments) will be required to have X-rays of their hands prior to the final study visit at 24-months.

Figure 7. Plain X-rays of the left hand showing a long oblique fracture of the 2nd metacarpal. *The hand was not implanted with Radiesse.*
A = anteroposterior view, B = lateral view.

The core lab radiologists will remain blinded to the study design, including any study timepoints that might involve Radiesse hand treatment. Timepoints will be listed by number of months from enrollment, and will not include any unblinding descriptors (e.g., injection visit). Further, the core lab radiologists will be asked to compare the prominence of any foreign material to that of the previous x-ray for that subject (where applicable). Consequently, documentation of the study timepoint associated with the x-ray image being read does not impact the integrity of the data reported by the core lab radiologists.

9.2 Visit schedule

Screening and Enrollment

Enrollment will be limited to 20 subjects for the study. The Sponsor will oversee enrollment and be in direct communication with the investigational site to make all efforts not to exceed the enrollment target of 20 subjects, and to ensure that Groups A and B (described in Section 7) are fully enrolled. Presenting subjects may be pre-screened to the selection criteria identified in Sections 7.2 and 7.3. If it is determined that a presenting subject meets these selection criteria, the subject will be given an Informed Consent Form to review and sign.

There will be 3 visits during the screening and enrollment period: 2 at the investigational site, and 1 at the local X-ray imaging center. The X-ray visit may be performed on the same day as the consent or injection.

Upon the subject's provision of informed consent to participate in the study, the subject will be enrolled in the study and assigned a study ID number. The number will contain 3 parts – trial identification code (XR = X-Ray), site identification number, and subject enrollment order number. For example, the third subject enrolled will receive study ID number XR-1-03. The masked evaluator will assess hands on the MHGS to meet hand rating requirements for inclusion. Enrolled subjects will be assigned to Group A or B based on baseline MHGS ratings until both groups are fully enrolled. Study information including demographics and concomitant medications will be recorded, and photographs will be taken of each hand. The subject will then be scheduled for hand X-rays to be taken prior to Radiesse hand treatment.

Within 72 hours after enrollment: Subjects will have X-rays taken of their hands at a designated, local, licensed imaging center.

Week 1/Initial treatment visit: 7 ± 6 days from enrollment, all subjects will return for a follow-up visit after completing the corresponding X-ray visit to the designated imaging center. This visit can be scheduled on the same day as the X-ray visit. Females of childbearing age will complete a urine pregnancy test. The subject's hands will be assessed on the MHGS by a live, masked evaluator. Subjects will complete the MHQ [REDACTED] [REDACTED]. At this time, subjects will receive a Radiesse treatment. A take-home 30-day diary will be given to the subject. A physician will assess the subject's hands for AEs. Photographs of the hands will be taken only in the event of a serious or medically concerning AE. Subjects will be scheduled for the Month 1 X-ray and follow-up visits.

Follow-Up Evaluations

72 hours after Week 1/initial treatment: Subjects will be scheduled for a phone visit 72 hours after treatment to assess for AEs. Subjects will be reminded to continue daily entries into their 30-day diary.

Month 1 X-rays: 30 ± 5 days from enrollment, all subjects will have x-rays taken of their hands at a designated, local, licensed imaging center. This visit must be completed prior to the Month 1 follow-up visit at the investigational site.

Month 1: 30 ± 5 days from initial treatment, all subjects will return for a follow-up visit after completing the corresponding X-ray visit to the designated imaging center. Changes in concomitant medications will be recorded by the study staff. The subject's hands will be assessed on the MHGS by a live, masked evaluator. Subject self-assessment of aesthetic improvement will be performed using the GAIS. Subjects will complete the MHQ [REDACTED].

[REDACTED] A physician will assess the subject's hands for AEs. The take-home 30-day diary will be reviewed for completion and

collected. A physician will assess the subject's hands for AEs. Photographs of the hands will be taken only in the event of a serious or medically concerning AE.

Month 6 X-rays: 180 ± 10 days from enrollment, all subjects will have X-rays taken of their hands at a designated, local, licensed imaging center. This visit must be completed prior to the Month 6 follow-up visit at the investigational site.

Month 6: 180 ± 10 days from enrollment, all subjects will return for a follow-up visit. Changes in concomitant medications will be recorded by the study staff. The subject's hands will be assessed on the MHGS by a live, masked evaluator. Subject self-assessment of aesthetic improvement will be performed using the GAIS. Subjects will complete the MHQ.

A physician will assess the subject's hands for AEs. A urine pregnancy test will be completed for female subjects of child bearing potential. A Radiesse retreatment will be performed on both hands if agreed upon by treating investigator and subject. A take-home 30-day diary will be given to the subject if a retreatment is received. Photographs of the hands will be taken only in the event of a serious or medically concerning AE.

72 hours after Month 6 retreatment: Only subjects receiving a retreatment at the Month 6 visit will be scheduled for a phone visit 72 hours after treatment to assess for adverse events. Subjects will be reminded to continue daily entries into their 30-day diary.

Month 7: $210 \text{ days} \pm 5$ days from enrollment, only subjects who received a retreatment at Month 6 will return for a follow-up visit. Changes in concomitant medications will be recorded by the study staff. The subject's hands will be assessed on the MHGS by a live, masked evaluator. Subject self-assessment of aesthetic improvement will be performed using the GAIS. Subjects will complete the MHQ.

A physician will assess the subject's hands for AEs. The take-home 30-day diary will be reviewed for completion and collected. Photographs of the hands will be taken only in the event of a serious or medically concerning AE.

Month 12 X-rays: 360 ± 10 days from enrollment, only subjects whose hand bones were not visible in the Month 6 X-rays will have X-rays taken of their hands at a designated, local, licensed imaging center. This visit must be completed prior to the Month 12 follow-up visit at the investigational site.

Month 12: 360 ± 10 days from enrollment, all subjects will return for a follow-up visit. Changes in concomitant medications will be recorded by the study staff. The subject's hands will be assessed on the MHGS by a live, masked evaluator. Subject self-assessment of aesthetic improvement will be performed using the GAIS. Subjects will complete the MHQ.

A physician will assess the subject's hands for AEs. A urine pregnancy test will be completed for female subjects of child bearing potential. A Radiesse retreatment will be performed on both hands if

agreed upon by treating investigator and subject. A take-home 30-day diary will be given to the subject if a retreatment is received. Photographs of the hands will be taken only in the event of a serious or medically concerning AE.

72 hours after Month 12 retreatment: Only subjects receiving a retreatment at the Month 12 visit will be scheduled for a phone visit 72 hours after treatment to assess for AEs. Subjects will be reminded to continue daily entries into their 30-day diary.

Month 13: $390 \text{ days} \pm 5 \text{ days}$ from enrollment, only subjects who received a retreatment at Month 12 will return for a follow-up visit. Changes in concomitant medications will be recorded by the study staff. The subject's hands will be assessed on the MHGS by a live, masked evaluator. Subject self-assessment of aesthetic improvement will be performed using the GAIS. Subjects will complete the MHQ.

A physician will assess the subject's hands for AEs. The take-home 30-day diary will be reviewed for completion and collected. Photographs of the hands will be taken only in the event of a serious or medically concerning AE.

Month 18: $540 \text{ days} \pm 10 \text{ days}$ from enrollment, all subjects will return for a follow-up visit. Changes in concomitant medications will be recorded by the study staff. The subject's hands will be assessed on the MHGS by a live, masked evaluator. Subject self-assessment of aesthetic improvement will be performed using the GAIS. Subjects will complete the MHQ.

A physician will assess the subject's hands for AEs. A urine pregnancy test will be completed for female subjects of child bearing potential. A Radiesse retreatment will be performed on both hands if agreed upon by treating investigator and subject. A take-home 30-day diary will be given to the subject if a retreatment is received. Photographs of the hands will be taken only in the event of a serious or medically concerning AE.

72 hours after Month 18 retreatment: Only subjects receiving a retreatment at the Month 18 visit will be scheduled for a phone visit 72 hours after treatment to assess for AEs. Subjects will be reminded to continue daily entries into their 30-day diary.

Month 19: $570 \text{ days} \pm 5 \text{ days}$ from enrollment, only subjects who received a retreatment at Month 18 will return for a follow-up visit. Changes in concomitant medications will be recorded by the study staff. The subject's hands will be assessed on the MHGS by a live, masked evaluator. Subject self-assessment of aesthetic improvement will be performed using the GAIS. Subjects will complete the MHQ.

A physician will assess the subject's hands for AEs. The take-home 30-day diary will be reviewed for completion and collected. Photographs of the hands will be taken only in the event of a serious or medically concerning AE.

Month 24 X-rays: $720 \text{ days} \pm 30 \text{ days}$ from enrollment, only subjects receiving a total of 4 treatments (initial, 6-, 12, and 18-months) will have X-rays taken of their hands at a

designated, local, licensed imaging center. This visit must be completed prior to the Month 24 follow-up visit at the investigational site.

Month 24: 720 ± 30 days from enrollment, all subjects will return for the final follow-up visit. Changes in concomitant medications will be recorded by the study staff. The subject's hands will be assessed on the MHGS by a live, masked evaluator. Subject self-assessment of aesthetic improvement will be performed using the GAIS. Subjects will complete the MHQ [REDACTED]. A urine pregnancy test will be completed for female subjects of child bearing potential. A physician will assess the subject's hands for AEs. Photographs of the hands will be taken. The subject's study participation will end at this visit.

Unscheduled Visits: Subjects will be instructed to call the investigational site if they experience significant hand discomfort or difficulty performing activities at any point during the 24 month period. At the discretion of the treating investigator, a subject will be requested to appear for an unscheduled study visit for follow-up and potential intervention for an AE of concern. For an unscheduled visit, the subject will be assessed for AEs, concomitant medication update will be obtained, the subject will complete an MHQ, and photographs of the hands will be taken.

Table 2. Schedule of Events.

Assessment	Screen -ing/ Enrollment	X-ray Wk 1	Wk 1†	Mo 1	X-ray Mo 6	Mo 6	Mo 7**	X-ray‡ Mo 12	Mo 12	Mo 13**	Mo 18	Mo 19**	X-ray* Mo 24	Mo 24
Visit Window (Day)	-7 to 0	Day 3 +- 3	Day 7 +0-7	Day 30 +5	Day 180 +10	Day 180 +10	Day 210 +5	Day 360 +10	Day 360 +10	Day 390 +5	Day 540 +10	Day 570 +5	Day 720 +30	Day 720 +30
Inclusion/ Exclusion	X													
Informed Consent	X													
Demographics	X													
Concomitant Medications	X			X		X	X		X	X	X	X		X
Merz Hand Grading Scale – Masked Evaluator	X			X		X	X		X	X	X	X		X
Michigan Hand Outcome Questionnaire			X	X		X	X		X	X	X	X		X

Subject GAIS			X		X	X		X	X	X	X		X	
Urine Pregnancy Test	Xα		Xα		Xα			Xα		Xα				Xα
X-rays of Hands		X		X††	X††			X‡					X*	
Hand Treatment			X			X ^v			X ^v		X ^v			
72-hour follow-up phone call			X			X**			X**		X**			
Adverse Events – Subject Diary		X	X	X		X**	X**		X**	X**	X**	X**		
Adverse Events – Treating MD		X	X	X		X	X		X	X	X	X		X
Hand Photographs	X		X‡‡	X‡‡		X‡‡	X‡‡		X‡‡	X‡‡	X‡‡	X‡‡		X

† To be scheduled after Week 1 X-ray, and can be on the same day after X-rays are taken

†† Corresponding X-ray imaging center visit must be completed prior to investigational site visit

* To be scheduled only for subjects receiving 4 treatments (enrollment, Months 6, 12, and 18)

** Only if repeat treatment received

‡ To be scheduled only if bones of at least 1 hand are not visible on Month 6 X-rays

‡‡ Only to document a serious or medically concerning adverse event

v Only if treatment is indicated as agreed upon by investigator and subject

α Prior to X-ray or Radiesse treatment

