1 SYNOPSIS

Study title

Radiesse® Post Approval Safety Study - Radiological Evaluation of Implantation in the Hands

Study phase

Device Post-Market

Study Product

Radiesse Injectable Implant

Indication

Hand augmentation to correct volume loss in the dorsum of the hand

Primary study objective

The objective of this study is to provide a preliminary assessment of the radiographic appearance of Radiesse material that has been injected into the dorsum of the hands. The assessment will be with standard, plain radiography (X-rays). The hypothesis is that the radiographic appearance of Radiesse in the hands does not obscure the bones of the hands as seen on plain X-rays of the hand.

Primary study endpoint

The primary endpoint is the safety assessment of the incidence of obscuration of the bones of the hand at 1-, 6-, 12-, and 24-months following injection of Radiesse in the dorsum of the hand.

Study population, diagnosis, and main criteria for in- and exclusion

The study will enroll 20 qualifying subjects at least 22 years of age with moderate to very severe volume loss in the dorsum of their hands based on the Merz Hand Grading Scale (MHGS¹, **Figure 1**), 10 with moderate to severe volume loss (MHGS grades 2 and 3) and 10 with very severe volume loss (MHGS grade 4). Key exclusion criteria include hands with previous fat injections, hand deformities, or surgery in the dorsum of the hands, and any medical condition with the potential to interfere with the study or increase the risk of adverse events (AEs). See Section 7 for the full list of inclusion and exclusion criteria.

¹ Carruthers, et al., “A Validated Hand Grading Scale,” Dermatol Surg 2008, 34:S179-S183.

Study design

This is a prospective, descriptive study designed to evaluate whether Radiesse interferes with radiological assessment by obscuring the bones of the hand.

Duration of treatment per subject

Subjects will be in the study for approximately 24 months. Subjects will be treated with Radiesse in the dorsum of the hands after baseline X-rays, and will have the opportunity to receive up to 3 repeat treatments over 2 years of follow-up. The retreatment interval is every six months as agreed upon by the treating investigator and the subject.

Total number of subjects and number of countries

There will be 20 subjects enrolled and treated in the United States.

Number of study sites

This will be a single-site study.

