6.1.1 Study visits

Subjects will be required to present for a total of up to 15 visits and 4 follow up phone calls. Of these visits, 7 to 10 are in-office investigational site visits and an additional 3 to 5 are X-ray visits at a licensed radiology center, and 1 to 4 are follow-up phone calls during their 24-month study participation.

If a subject only receives the initial treatment at enrollment, there will be a total of 7 in-office clinic visits, 3 x-ray visits and 1 follow-up phone call. For each of the 3 optional repeat treatments received, there will be an additional follow-up phone call (72 hours post injection). The fourth x-ray visit will only be required at Month 12 if no bones are visible

at the 6 month x-ray and the fifth x-ray visit will only be conducted if a subject receives four total treatments of Radiesse in this PAS study.

Following consent and enrollment at the site, subjects will have X-rays taken of their hands at the radiology imaging center. Each digital radiographic image taken in the study will be assessed by 2 independent blinded, licensed radiologists at the radiology core lab. After X-rays, all subjects will return to the study clinic to receive Radiesse treatment.

At 1-month, all subjects will have X-rays of their hands taken and will be assessed by the treating investigator for AEs.

At 6-months after enrollment, all subjects will have X-rays of their hands taken prior to receiving a repeat Radiesse treatment, if Radiesse retreatment is agreed upon by treating investigator and subject.

Subjects will have X-rays of their hands at 12-months only if bones of the hands were reported to be obscured by Radiesse by at least 1 radiologist on the 6-month X-rays, and will be assessed by the treating investigator for AEs. Subjects will receive repeat Radiesse treatments at 12- and 18-month follow-up visits if Radiesse retreatment is agreed upon by treating investigator and subject. If X-rays of the hands are required at 12 months, they will be taken prior to Radiesse retreatment.

Subjects will have X-rays at 24-months only if they receive 4 Radiesse treatments in the study; at enrollment, 6-, 12-, and 18-months after enrollment.

An additional 1-month follow-up visit and 72-hour follow-up phone call will be scheduled after each repeat treatment received at the 6-, 12-, and 18-month visits which would be at 7-, 13-, and 19-months, respectively.

6.1.2 *End of study*

[figure not shown]

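### The Month 1 X-ray is timed from enrollment, so on target it falls 23 days after injection rather than 30; the 1-month post-retreatment visits share the enrollment anchor and can fall 15 to 45 days after retreatment.

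*Protocol*

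**What the plan says.** The Protocol synopsis defines the primary endpoint as obscuration "at 1-, 6-, 12-, and 24-months following injection of Radiesse in the dorsum of the hand". Protocol Section 4.2 and SAP Section 2 likewise place the first two post-baseline X-rays 1 and 6 months after treatment. Protocol Sections 5.2 and 12.3.1 and SAP Section 6.1 list 1, 6, 12 and 24 months without naming a time origin.

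Protocol Section 9.2 sets the dates for the first cycle:

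- First injection: "Week 1/Initial treatment visit: 7 ± 6 days from enrollment".
- Month 1 X-ray: "30 ± 5 days from enrollment, all subjects will have x-rays taken of their hands", to be completed before the clinic visit.
- Month 1 clinic visit: "30 ± 5 days from initial treatment, all subjects will return for a follow-up visit".

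Table 2 puts the Month 1 X-ray and clinic assessments in one column at Day 30. It also gives a different window for the first treatment: Day 7, plus 0 minus 7.

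For retreatment, Section 6.1.1 says "An additional 1-month follow-up visit and 72-hour follow-up phone call will be scheduled after each repeat treatment received" and places these visits at Months 7, 13 and 19. Section 9.2 counts both ends of the interval from enrollment. The retreatment visit is "Month 6: 180 ± 10 days from enrollment, all subjects will return for a follow-up visit", and Month 7 is 210 ± 5 "days from enrollment, only subjects who received a retreatment at Month 6 will return for a follow-up visit". Months 13 (390 ± 5) and 19 (570 ± 5) follow the same pattern. Yet Sections 5.2 and 12.3.2 and SAP Section 6.4 define MHGS and GAIS outcomes at 1 month after retreatment.

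**The concern.** The X-ray and the clinic visit that it precedes carry the same Month 1 label but run on different clocks. Treatment comes a nominal week after enrollment, so the X-ray clock starts a week early. The shift is minor at Month 6 (7 days in 180) but is nearly a quarter of the nominal interval at Month 1 (7 in 30).

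The Month 12 and Month 24 X-rays are conditional, so Months 1 and 6 are the only post-treatment images planned for all 20 subjects. The primary variable and its exact confidence intervals are reported by visit, so one of the two complete time points would carry the wrong label. The variation in time since injection would also go unreported.

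After retreatment, a visit at the short end of the range assesses MHGS and GAIS well before one month. It also collects a 30-day diary before 30 days have passed.

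**Working it through.** **Inputs, as days from enrollment (Protocol Section 9.2).** First treatment: target 7, window 1–13. Month 1 X-ray: target 30, window 25–35. Month 1 clinic visit: treatment day + 30, window + 25 to + 35. Retreatment at Month 6: target 180, window 170–190. Month 7 visit: target 210, window 205–215. Months 12/13 and 18/19 repeat the last pair 180 and 360 days later.

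**Formula.** Interval = assessment day − day of the preceding injection. The extremes are earliest assessment − latest injection, and latest assessment − earliest injection.

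**The plan's own figure.** One month, taken as 30 ± 5 days after injection. The clinic visit reproduces it: treatment on Day 7 puts the visit on Day 37, and 37 − 7 = 30. The X-ray does not.

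| Interval | On target | Range |
|---|---|---|
| Injection to Month 1 X-ray, Section 9.2 | 30 − 7 = 23 | 25 − 13 = 12 to 35 − 1 = 34 |
| Same, Table 2 treatment window (Day 0–7), X-ray ± 5 | 23 | 25 − 7 = 18 to 35 − 0 = 35 |
| Same, Table 2 with Month 1 read literally as Day 30 + 5 | 23 | 30 − 7 = 23 to 35 − 0 = 35 |
| Month 1 X-ray to its clinic visit, Section 9.2 | 37 − 30 = 7 | 0 to (13 + 35) − 25 = 23 |
| Retreatment to Month 7, Section 9.2 | 210 − 180 = 30 | 205 − 190 = 15 to 215 − 170 = 45 |
| Same, Table 2 read literally | 30 | 210 − 190 = 20 to 215 − 180 = 35 |

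The plus signs in Table 2 may be ± signs lost in text extraction, so both readings are shown. The conflict within Section 9.2 does not depend on either. Months 13 and 19 give the same ranges as Month 7.

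**Treatment on target (Day 7).** An in-window X-ray falls 25 − 7 = 18 to 35 − 7 = 28 days after injection, so it can never reach 30. Only Days 32–35 (4 of 11) are at least 25 days after injection.

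**Late treatment.** With treatment on Day 11, 12 or 13, the clinic window opens on Day 36, 37 or 38, after the X-ray window has closed on Day 35. The two visits then cannot share a day in window.

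**Illustration only.** Suppose every in-window day is equally likely and visits are independent. For the Month 1 X-ray, 13 × 11 = 143 combinations are possible: 88 (62%) fall under 25 days and 55 within 25–35. For Month 7, 21 × 11 = 231 are possible: 55 (24%) fall under 25 days, 15 of those (6% of 231) under 20; 121 (52%) fall within 25–35 and 55 over 35. The documents give no attendance data, so these are not forecasts.

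**The case against.** **The endpoint's origin is less settled than it looks.** The operative endpoint definitions name no anchor, and Section 9.1.4 labels core-lab time points by months from enrollment. However, the synopsis, Section 4.2 and SAP Section 2 all count from injection or treatment, and no definition of the primary endpoint counts from enrollment. The core-lab labels serve blinding and can stay.

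**Sites may treat early.** The baseline X-ray may be on the day of consent or of injection. Treatment on Days 1–5 gives an on-target X-ray at 25–29 days. That is possible, but the stated target is Day 7 and Section 9.2 allows up to Day 13. The 12-day extreme does need a treatment day that Table 2 excludes.

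**The retreatment visits are not shifted.** This stands. Both visits are counted from enrollment, so the on-target interval is right, and 15 or 45 days requires two visits at opposite window limits. No X-ray is scheduled at these visits, so the primary endpoint is untouched. The fault there is spread only.

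**Non-overlapping windows are still workable.** This also stands: the protocol requires only that the X-ray come first.

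**Little turns on it.** The study is descriptive and has no planned hypothesis tests. With 20 subjects, even 0 of 20 has a 95% exact upper limit of 1 − 0.025^(1/20) ≈ 17%. The documents do not show which way a week's difference would move obscuration. Obscuration at any time is little affected, and adverse events must be recorded through the last visit even if diary days are lost. These points limit the severity. They do not make the by-visit label correct.

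**Conclusion.** The concern holds. Followed as written, Section 9.2 places the Month 1 X-ray 23 days after injection on target (12 to 34 by its windows, a spread of 22 days), while the synopsis promises 1 month after injection. Table 2 gives the same 23 days on target. The 1-month post-retreatment visits have the same anchor but a different effect: a correct 30 days on target, with a range of 15 to 45. The SAP contains nothing that corrects or discloses either.

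The 23 days rests only on the stated targets, and the ranges only on the stated windows. No direction of bias in obscuration is claimed. The first-cycle clinic assessments and first diary are already counted from injection and are unaffected. This should be corrected because it changes when a primary-endpoint image is taken, but it does not threaten the study's overall conclusion.

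**What to change.** - In Protocol Section 9.2, time the Month 1 X-ray from the initial injection, as the Month 1 clinic visit already is. With the same 30 ± 5 days, the interval becomes 25–35 days, with a target of Day 37 from enrollment (Days 26–48 across the Section 9.2 treatment window).
- Time the Month 7, 13 and 19 assessments from the actual retreatment date. With ± 5 days, the interval becomes 25–35 instead of 15–45.
- Reconcile Section 9.2 with Table 2, including the two different windows for the initial treatment and the shared Month 1 column.
- If a 1-month visit falls before diary day 30, let the subject keep the diary and return it once complete.
- In the SAP, state the time origin, and derive and report days since last injection for each X-ray and each 1-month assessment. Even if the visits were not re-anchored, this would make the true timing visible.

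The cost is protocol wording and one derived variable from dates the study records anyway. There are no extra X-rays, visits or radiation. Calendar scheduling becomes slightly less uniform, and some diaries come back after the visit.
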